Because it is possible that prior exposure will impact the relative impact of peptide specific help on the antibody response, subjects will be screened for pre-vaccination antibody. Subjects will be divided into relatively high (greater than 1:8) or low (equal to or less than 1:8) pre-vaccination antibody based on pH1N1. The basic study design for the healthy adults age 18-49 years is described below. Subjects will be queried regarding prior history of influenza vaccination, and stratified into those who have not been vaccinated in the previous year and those who have, followed by randomized assignment to receive one of four licensed vaccines. Study subjects who participated in a previous year can be re-enrolled and will receive the same vaccine they received previously. Because the goal of the protocol is to evaluate the immune response to the vaccine and is not intended as a formal comparison of the adverse event profile, the vaccine assignment is not blinded. Following vaccination, subjects will have samples of blood obtained at the time points illustrated above. The last study visit will take place approximately 6 months after vaccination in order to test the durability of the response.

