4.2 Outcome Measures

4.2.1 Primary Outcome Measures

The primary outcome measure for this study is:

- Mean change in the specificity, quantity and quality of serum antibody titers to the vaccine viruses, pH1N1, H3 and influenza B using HAI (year 1-5) and MN for pH1N1 and H3 viruses (years 1-5 from Day 0 to Day 28)

- Mean change in the CD4 T cell reactivity to pools of total pHA peptides derived from the pH1N1 HA, as well as H3, influenza B HA, NP, and M1 peptides will be quantified using cytokine Elispot From Day 0 to Day 14

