8.3.4 Day 28 visit (\pm 2 days)

Subjects will return for follow up approximately 28 days after vaccination for assessment of the immune response. At that visit, the following procedures will be performed:

- Interval medical history will be obtained including concomitant medications, reviewing any new events since the last visit
-

-
- If indicated by medical history, a directed physical exam will also be performed.
 - Any adverse events (AE) will be recorded as described in the safety section 10.1 and appropriate corrective actions taken if indicated
 - A serum sample will be obtained from an arm vein for antibody titers
 - Peripheral Blood Mononuclear Cells (PBMC) will be collected from an arm vein for assessment of the B cell response to vaccination

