8.3.6 Final study visit (Day 180 +/- 14 days)

Subjects will return approximately 180 days after vaccination for follow-up. This visit will be the study termination visit. At the final visit the following procedures will take place:

- Interval medical history will be obtained, including concomitant medications, reviewing any new events since the last visit
 - If indicated by medical history, a directed physical exam will also be performed.
 - Adverse events (AE) will be recorded and corrective actions taken if indicated
-

- A serum sample will be obtained from an arm vein for antibody titers
- Peripheral Blood Mononuclear Cells (PBMC) will be collected from an arm vein for assessment of the CD4 T cell response to vaccination

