9.2 Laboratory Evaluations/Assays

9.2.1 Immunogenicity Evaluations

Serum hemagglutination-inhibition (HAI). HAI will be performed in microtiter format using turkey RBCs and egg-grown, betapropiolactone-inactivated A/California/07/09 virus as antigen. The titer of antibody will be defined as the highest dilution resulting in complete inhibition of hemagglutination. Sera will be treated with receptor-destroying enzyme and heat inactivated prior to testing at an initial starting dilution of 1:4. Sera with no detectable HAI titer will be assigned a titer of 1:2 for calculation purposes.

Microneutralization (MN) assay: Sera will be tested by microtiter technique for neutralization of an A/California/07/09 x PR8 reassortant virus in MDCK cells. Viral growth will be determined by ELISA of the cells following fixation with methanol using a combination of M- and NP-specific monoclonal antibodies. The titer of antibody will be defined as the highest titer resulting in 50% inhibition of antigen signal compared to un-neutralized control wells. Sera will be treated with RDE and heat inactivated prior to testing at an initial starting dilution of 1:10. Sera with no neutralizing titer will be assigned a value of 1:5 for calculation purposes.

B cell responses: Peripheral Blood Mononuclear Cells (PBMC) will be obtained before and on day 7 and 28 after vaccine and evaluated for B-cell responses. B cell responses will be evaluated by memory cell assay [16] and antibody secreting cell assay. In addition, B cells will be cultured in vitro and the functional quality of secreted antibody assessed by HAI and MN assays

CD4 T cell responses: PBMCs collected prior to and on day 3, 7, 14 and 180 after vaccination will be evaluated for the presence of antigen specific CD4 cells by ELISPOT assay and flow cytometry using a panel of peptides spanning the H1 hemagglutinin, neuraminidase and internal virion proteins such as NP and M1 [17]. This assay will identify both cross reactive and H1 specific epitope responses, as well as recall of memory cells to conserved internal virion proteins. PBMC will also be evaluated for the presence of antigen specific ELISPOT and cell homing markers by flow cytometry.

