12.4 Final Analysis Plan

We will define the groups as: G1 (egg derived vaccine) = G1a (seronegative to pH1N1 virus and receiving egg derived vaccine) + G1b (seropositive and receiving egg derived vaccine); G2 (baculovirus derived vaccine) = G2a (seronegative to to pH1N1 virus and receiving baculovirus derived vaccine) + G2b (seropositive and receiving baculovirus derived vaccine). The log transformation will be applied to stabilize variance, as suggested by our past experience [18]. The between-group and among-group comparison in each of the outcomes will be based on both standard statistical analysis approaches using summary statistics and the complicated random variance model approach. Specifically, each of CD4 specific cells for different Influenza proteins (eg HA, NP etc), memory B cell derived polyclonal antibodies, HAI and MN titers among the four groups and between G1 and G2, between G1a and G2a, and between G1b and G2b, we will use maximum responses or maximum boost responses (maximum value after day 0 – value at day 0) or maximum fold increase as endpoint and do group comparison by ANOVA for among-group comparison and two-sample t-test for between-group comparison, or their nonparametric analogy of Kruskal-Wallis test and Wilcoxon Rank sum test, respectively, may also be applied for robustness. Multiple comparisons may subject to Bonferroni correction, if appropriate. Correlation test such as Pearson correlation analysis, or its nonparametric analogy of Spearman correlation analysis, will be used to study how baseline CD4 responses and/or memory B cell derived polyclonal antibodies, HAI, MN titers affect the boost responses of CD4, memory B cell derived polyclonal antibodies, HAI and MN titers after vaccination.

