Various parametric or nonparametric mixed-effects regression approaches will be used to study the dynamic curve of each outcome, to take account of the correlation among observations from the same subjects over time. Group indicator will enter the model as a predictor and thus can be compared simultaneous at each time point and also by difference from difference approach to control the effect of baseline values. Demographic information may be controlled by entering the model as predictors. To further investigate the effect of CD4 cell specificity in helping neutralizing antibody responses, regression analysis will be applied, with boost or fold increase of HAI or MN titers as responses, all the CD4 cell specificities as predictor, possibly adjusting demographic variables. Type I and III sum of squares and standard coefficient estimates can be used to compare the effect of CD4 specificities in helping neutralizing antibody responses. The parametric or nonparametric mixed-effects regression approaches may also be used to compare the effects to take account of within-subject correlation. Among-group plasmablast comparisons will be proceeded by: 1). One-way ANOVA, or its nonparametric analog of Kruskal-Wallis test; 2). Repeated ANOVA or its nonparametric analog of Friedman test for simultaneous pairwise comparison, with within-subject correlation taken into account.

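### The group tests in 12.4 use an unwindowed maximum response, not the Day 14 and Day 28 changes that 4.2.1 makes primary, and no analysis is named primary

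*Combined protocol and SAP*

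**What the plan says.** Section 4.2.1 defines both primary outcomes as mean changes between two stated days. For antibody the measurement is made "using HAI (year 1-5) and MN for pH1N1 and H3 viruses (years 1-5 from Day 0 to Day 28"; for CD4 T cells the reactivity "will be quantified using cytokine Elispot From Day 0 to Day 14".

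The first analysis in section 12.4, ANOVA across groups and a two-sample t-test between groups (or their rank-based counterparts), has a different endpoint: "we will use maximum responses or maximum boost responses (maximum value after day 0" minus the Day 0 value), or the maximum fold increase. No last visit is set and none of the three is chosen.

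The samples available to that maximum are:
- CD4, section 9.2.1: "PBMCs collected prior to and on day 3, 7, 14 and 180 after vaccination will be evaluated".
- Serum, Day 28 (section 8.3.4): "A serum sample will be obtained from an arm vein for antibody titers". The final visit (section 8.3.6, "Subjects will return approximately 180 days after vaccination for follow-up") also takes serum. The procedures table in section 19 shows no other post-vaccination serum.

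The Protocol Summary gives the purpose of the late visit: "The last study visit will take place approximately 6 months after vaccination in order to test the durability of the response". Section 12.4 does not exclude it from the maximum.

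Section 12.4 also plans mixed-effects models in which groups can be "compared simultaneous at each time point and also by difference from difference approach to control the effect of baseline values". It names no visit for them, and it calls no analysis primary.

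**The concern.** A maximum over visits and a change to a fixed day are different estimands. A stated analysis rule therefore tests something other than the declared primary outcome, and the plan does not say which result answers the primary objective if they differ. Section 12.3.2 has immunogenicity analysed yearly, so results accumulate while the choice is open.

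For antibody there is a further problem. Follow-up includes the influenza season (section 8.3.5), so a Day 180 titre may reflect infection. An unwindowed maximum would count that rise as vaccine response.

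**Working it through.** **1. The two definitions side by side**

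| Outcome | 4.2.1 | 12.4 tests | Visits the maximum can use | When they coincide |
|---|---|---|---|---|
| CD4 ELISPOT | Day 14 − Day 0 | maximum after Day 0 | 3, 7, 14, 180 | not in general, even without Day 180 |
| HAI, MN | Day 28 − Day 0 | maximum after Day 0 | 28, 180 | boost or fold form, only if Day 180 is excluded |

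On the log scale the maximum boost equals the log of the maximum fold increase. The maximum response is different again, because it ignores baseline.

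**2. The plan's own figure**

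Section 12.2 claims 80% power for a 10–20% difference with 45 per group, CV 0.25–0.4 and a two-sided 0.05 t-test. The detectable difference is (1.960 + 0.842) × CV × √(2/45) = 0.591 × CV, which is 14.8% at CV 0.25 and 23.6% at CV 0.4. On the log scale it is an increase of 15.8% or 25.9%, or a decrease of 13.7% or 20.6%. The 10% end is not reproduced. That is a separate matter: 12.2 names no visit or summary measure, so it does not settle this point.

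**3. CD4: Day 14 change against maximum boost**

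From section 12.2: 45 per group, CV 0.25–0.4, log scale, two-sided t-test. Assumed: true ratio 1.25 at the visits where arms differ, and correlation 0.5 between all visits. Simulated log-normal counts at Days 0, 3, 7, 14 and 180, with σ = √ln(1 + CV²) = 0.246 or 0.385.

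Closed-form check at CV 0.4: SD of the change = 0.385 × √(2 × (1 − 0.5)) = 0.385; SE = 0.385 × √(2/45) = 0.0812; ln 1.25 / SE = 0.223 / 0.0812 = 2.75, giving power of about 0.78.

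Profiles are mean fold rises at Days 3/7/14/180: flat 1.6 throughout; plateau 1.2/1.6/1.6/1.1; Day 14 peak 1.2/1.6/2.0/1.1; Day 7 peak 1.2/2.0/1.6/1.1. Power is shown for CV 0.4, then CV 0.25.

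| Arms differ at | Profile | Day 14 change | Maximum boost |
|---|---|---|---|
| Day 14 only | flat | 0.78, 0.99 | 0.21, 0.57 |
| Day 14 only | plateau | 0.78, 0.99 | 0.38, 0.85 |
| Day 14 only | Day 14 peak | 0.77, 0.99 | 0.61, 0.98 |
| Day 14 only | Day 7 peak | 0.78, 0.99 | 0.19, 0.32 |
| Day 7 only | flat | 0.05, 0.05 | 0.21, 0.57 |
| Day 7 only | Day 7 peak | 0.05, 0.05 | 0.61, 0.98 |
| all visits | flat | 0.78, 0.99 | 0.88, 1.00 |
| none | flat | 0.05, 0.05 | 0.05, 0.05 |

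Dropping Day 180 from the maximum in the first row gives 0.29 and 0.70, so the discrepancy is not only a Day 180 matter.

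**4. Antibody: Day 28 change against maximum boost**

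All inputs except 45 per group are assumed. Mid-range: log2 titre SD 1.25, correlation 0.6, waning of 1 log2 by Day 180, rise of 2.5 log2 if infected. Maximum boost = max(Day 28, Day 180) − Day 0.

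The Day 28 change has SD 1.25 × √(2 × (1 − 0.6)) = 1.118 and SE 1.118 × √(2/45) = 0.236. A true difference of 0.75 log2 gives 0.75 / 0.236 = 3.18, or power 0.88, whatever the infection rates.

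| Infected, stronger / weaker arm | Maximum-boost difference, true 0.50 | Maximum-boost power, true 0.75 | Maximum-boost rejection, true 0 |
|---|---|---|---|
| 0 / 0% | 0.50 | 0.91 | 5% |
| 10 / 10% | 0.50 | 0.87 | 5% |
| 5 / 10% | 0.43 | 0.81 | 6% |
| 5 / 15% | 0.36 | 0.70 | 9% |
| 10 / 5% | 0.57 | 0.93 | 6% |
| 15 / 5% | 0.64 | 0.96 | 9% |

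In the last column there is no stronger arm; the rates are simply those of the two arms. Over 81 combinations (waning 0–2, rise 2–3, SD 1.0–1.5, correlation 0.5–0.7) a true 0.50 becomes 0.37–0.48 at 5/10% and 0.23–0.47 at 5/15%.

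**The case against.** **The mixed models already cover it.** Compared at Day 14 and Day 28, the models in 12.4 give the 4.2.1 contrasts, so the primary outcomes are not left without an analysis. That stands. But several model types are offered, no visit is named, and none is given precedence over the tests on the maximum.

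**Section 12.2 identifies the test.** It ties the primary aim to egg-derived against baculovirus-derived vaccine, log counts and a two-sample t-test. It does not say at which visit or on which summary.

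**The CD4 power loss comes from extreme cases.** This has force. If arms differ at both Day 7 and Day 14 (CV 0.4), the Day 14 change and the maximum have power 0.77 and 0.79 (plateau), 0.78 and 0.80 (Day 14 peak), and 0.78 and 0.81 (Day 7 peak). Only the flat profile shows a loss, 0.78 against 0.51. The power figures show that the measures can disagree, not that the maximum is generally worse.

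**The infection rates are invented, and titres are strain-specific.** At 1/2% or 2/4% infected, a true 0.50 becomes 0.49 or 0.47, and power for 0.75 is 0.90 or 0.87 against 0.88. Material antibody bias needs a sizeable imbalance between arms.

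**A peak suits T cells.** Sections 8.3.1 and 8.3.2 call timing critical at Days 3 and 7, and a Day 14 test misses a Day 7-only difference. Either section could be changed to match the other. This supports keeping a defined maximum; it does not support leaving the choice open. Nor does the study's description of itself as explorative, since 4.2.1 still declares primary outcomes.

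**Conclusion.** The concern holds. The ANOVA and t-test in 12.4 do not test the outcomes that 4.2.1 declares primary, the maximum has no window and three forms, and no analysis is named primary. This follows from the text alone and should be fixed.

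The size depends on assumptions. Only the CV range and the 45 per group come from the documents. For CD4 the maximum can have far less power than the Day 14 change, about the same, or more, depending on when the arms differ and on the shape of the response. For antibody there is no material bias if infection between Days 28 and 180 is absent or equal between arms. If it is unequal, the maximum shifts toward the more infected arm: a true 0.50 log2 becomes 0.36 or 0.64 at 5% against 15%, with mid-range inputs. A single prespecified maximum test keeps about 5% error when infection is equal, and rejects about 9% of the time at 5% against 15% when there is no Day 28 difference.

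**What to change.** In section 12.4:
- State that the primary analyses are the log change from Day 0 to Day 28 for HAI and MN, and from Day 0 to Day 14 for ELISPOT. Give each one named test, or the corresponding mixed-model contrast.
- Keep one CD4 maximum, in one stated form over Days 3, 7 and 14, labelled secondary.
- Drop the serum maximum. Limited to Day 28, the maximum boost is identical to the primary change.
- Analyse Day 180 as durability. Flag samples taken after PCR-confirmed influenza (swabs are already taken under section 8.3.5) and add a sensitivity analysis without them.

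The cost is analysis-plan wording; all the samples are already scheduled. CD4 responses peaking at Day 3 or Day 7 would be captured only in the secondary analysis. If arms differ equally at all visits, the Day 14 test gives up some power (0.78 against 0.88 at CV 0.4 and correlation 0.5).

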4 OBJECTIVES AND OUTCOME MEASURES

4.1 Study Objectives

Primary Objective

- Comparison of the serum antibody response to immunization with pure HA, cell-derived and egg derived subvirion vaccines in adults age 18-49 years
- Comparison of the HA- specific CD4 T cell response in adults receiving pure HA, cell-derived vaccine egg-derived split or subvirion vaccines

Secondary Objectives

- Comparison of the epitope specificity of B cells following vaccination with HA or subvirion vaccines

Evaluation of the different vaccine formulations to induce HA specific antibodies that recognize circulating viruses

Exploratory Objective

- Confirmation of the safety of the licensed vaccines in healthy adults
-
- Evaluation of the effect of repeated vaccination on the immune response

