4.2.2 Secondary Outcome Measures

Secondary and tertiary outcome measures are listed below:

Secondary Outcome Measures

[figure not shown]
- Antibody specificity of cloned plasmablasts from subjects in each group
-
- Correlations of CD4 T cell ELISPOT number (Day 0 to Day 14) and antibody titers (Day 0 to Day 28) in subjects from each group (year 1-3), R value per cohort will be reported

Tertiary Outcome Measure

- Vaccine related adverse events
- Mean change in the CD4 T cell reactivity to pools of total pHA peptides derived from the pH1N1 HA, as well as H3, influenza B HA, NP, and M1 peptides will be quantified using cytokine Elispot from Day 0 to Day 14 for subjects with successive years of vaccination

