5 STUDY DESIGN

Subjects age 18-49 years will be stratified by their prior vaccination history, followed by randomized assignment to receive one of three licensed vaccines: Fluzone SD, Fluzone HD and Flublok. Block randomization will be performed separately for the two groups. Study subjects who participated in a previous year can be re-enrolled and receive the same vaccine as previously (Fluzone SD, Fluzone HD, Flublok, Flucelvax). Because the goal of the protocol is to evaluate the immune response to the vaccine and is not intended as a formal comparison of the adverse event profile, the vaccine assignment is not blinded. Following vaccination, subjects will have blood sample obtained at the time points illustrated above. The last study visit will take place 6 months after vaccination.

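### Section 12.4 leaves out the prior-vaccination stratum used in randomisation and does not say whether returners' later, non-re-randomised seasons enter the main vaccine comparison

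*Combined protocol and SAP*

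**What the plan says.** **Randomisation.** Section 5 stratifies new subjects by vaccination history and states: "Block randomization will be performed separately for the two groups". Section 3.2 shows that this stratifier came in after the first full year, in place of screening for low pH1N1 titres.

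**Returners.** Section 5 adds: "Study subjects who participated in a previous year can be re-enrolled and receive the same vaccine as previously". Section 8.2 agrees, so a returner's later season carries no new randomisation.

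**Analysis.** Section 12.4 defines egg-derived (G1) and baculovirus-derived (G2) groups, each split by pH1N1 serostatus. For the endpoints it will "do group comparison by ANOVA for among-group comparison and two-sample t-test for between-group comparison", or the rank analogues. It also names a random variance model without defining it. The mixed models carry a group indicator and a "difference from difference approach to control the effect of baseline values". On covariates the text is: "Demographic information may be controlled by entering the model as predictors". Season, the prior-vaccination stratum, returners and an analysis set are not mentioned.

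**Where returners do appear.** Section 4.1 lists as exploratory: "Evaluation of the effect of repeated vaccination on the immune response". Section 4.2.2 has a tertiary CD4 outcome "from Day 0 to Day 14 for subjects with successive years of vaccination". No antibody outcome is named for them. The primary antibody outcome in Section 4.2.1 is measured "using HAI (year 1-5) and MN for pH1N1 and H3 viruses", with no statement about returners. Section 12.3.2 says immunogenicity is analysed yearly, without a rule for combining years.

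**The concern.** Two gaps sit together.

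First, the factor used to randomise is missing from the analysis. Section 3.1 calls it prognostic for antibody response, and Section 3.2 reports that the first full year was imbalanced on it. A test that ignores a prognostic stratum used in allocation carries a standard error that is too large for the design.

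Second, the set of records in the main comparison is undefined. A returner from the preceding season is by definition previously vaccinated. If returners are counted beside new subjects, arms with different shares of returners can differ for a reason other than the vaccine, even within one season. Fluzone HD was added after the first full year, so in its first season it can have no HD returners, while Fluzone SD and Flublok can have returners. After Flucelvax closed to new subjects, all its recipients are returners. Baseline differencing does not by itself remove this, because it compares rises, and the response to revaccination is what Section 3.1 describes as weaker.

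**Working it through.** **The plan's own figure.** Section 12.2 gives 45 per group, 80% power, two-sided 0.05, two-sample t-test. The detectable standardised difference is (1.960 + 0.842) × √(2/45) = 0.591 by normal approximation, or 0.597 by the exact t calculation. With the stated CV of 0.25-0.4 on the raw scale, 0.597 × CV = 14.9%-23.9%, not the stated 10%-20%. That mismatch is a separate matter and nothing below depends on it.

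**1. Omitting the stratum, newly randomised subjects only.** The documents give no stratum effect, so 0.5 and 1.0 within-stratum SD are assumed. With a share p in one stratum and effect d, the between-stratum variance is v = p(1−p)d². Stratified allocation removes v from the true error of the difference, but the unadjusted test leaves it in the estimated error. Hence true error ≈ 2[1 − Φ(1.96 × √(1+v))]. The closed form is set beside a simulation of 40,000 trials (45 per arm, effect 0.591 SD):

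| p | d | v | error, formula | error, simulated | power unadjusted | power with stratum | loss (points) |
|---|---|---|---|---|---|---|---|
| 0.50 | 0.5 | 0.063 | 4.3% | 4.1% | 77.5% | 79.2% | 1.7 |
| 0.50 | 1.0 | 0.250 | 2.8% | 2.9% | 71.3% | 79.0% | 7.7 |
| 0.67 | 0.5 | 0.055 | 4.4% | 4.4% | 77.5% | 79.1% | 1.6 |
| 0.67 | 1.0 | 0.221 | 3.0% | 2.9% | 72.5% | 79.1% | 6.6 |

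**2. First full year, before this stratification.** Section 3.2 gives prior vaccination as 18/22 (82%) for Fluzone, 16/22 (73%) for Flublok and 13/26 (50%) for Flucelvax. The three-group chi-square p is 0.052. Fisher p is 0.034 for Fluzone against Flucelvax and 0.72 for Fluzone against Flublok. Here adjustment addresses chance imbalance as well as precision.

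**3. Returners mixed in, within HD's first season.** Assumed: a fraction q = 0.25-0.75 of the 22 first-year subjects in each of Fluzone and Flublok return; n = 22-45 new subjects per arm; all returners count as previously vaccinated; new recruits are previously vaccinated at the first-year rate, (18+16+13)/(22+22+26) = 47/70 = 67.1%. That rate is for a history of vaccination, whereas the design text after the Protocol Summary defines the stratum by the previous year, so it is only a stand-in.

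- Returner share in SD or Flublok = 22q/(22q+n): 5.5/50.5 = 10.9% to 16.5/38.5 = 42.9%. In HD it is 0.
- Gap in prior vaccination against HD = share × (1 − 0.671): 3.6 to 14.1 points.
- If HD counts within G1, the G1 share = 22q/(22q+2n): 5.5/95.5 = 5.8% to 16.5/60.5 = 27.3%. The G1 versus G2 gap is then (10.9 − 5.8) × 0.329 = 1.7 points to (42.9 − 27.3) × 0.329 = 5.1 points.
- If prior vaccination lowers the log2 fold rise by 0.5-1.5 (assumed), the fold-rise ratio shifts by 2^(0.5×0.036) = 1.01 to 2^(1.5×0.141) = 1.16 for HD against SD or Flublok, and by 2^(0.5×0.017) = 1.006 to 2^(1.5×0.051) = 1.055 for G1 against G2.

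**4. Only if seasons are pooled and person-seasons treated as independent.** With m seasons per person and between-season correlation r (not given), the design effect is 1 + r(Σm²/Σm − 1). If a quarter return once, Σm²/Σm = 1.75/1.25 = 1.40. If half do, it is 2.5/1.5 = 1.667. The true error of a nominal 5% test, 2[1 − Φ(1.96/√deff)], is 5.0%-8.3% and 5.0%-10.6% respectively for r = 0 to 0.7. At r = 0.1 it is 5.5% and 5.8%.

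**The case against.** The best reply has four parts.

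- **The unadjusted t-test is the test that was powered.** Section 12.2 sizes the study on it, for CD4 counts, and does not say that its CV is within-stratum. This stands. A reader might infer that omitting the stratum leaves the trial short of 80% power. The documents do not support that: what is shown is precision forgone. Section 3.1 speaks of antibody, and no prior-vaccination effect on CD4 is given anywhere.
- **Serostatus comparisons are a partial control.** Section 3.1 links prior vaccination to higher baseline titres, and Section 12.4 compares G1a with G2a and G1b with G2b. This is true but weak, because Section 3.2 reports that few subjects with titres of 1:8 or below could be found.
- **Returners have their own purpose.** Sections 3.2, 3.3, 4.1 and 4.2.2 point to a separate repeat-vaccination aim. A reader might infer that the plan intends to mix returners into the main comparison. It does not say so. The gap is an unstated rule.
- **HD contrasts are not named in Section 12.4.** Its groups are egg and baculovirus only, and the hypothesis in Section 12.1 is egg-derived versus recombinant. This stands, and the larger shift for HD should not be read as applying to the main hypothesis. It still matters for the aim in Section 3.2 of separating dose from composition.

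Yearly analysis (Section 12.3.2) would remove season confounding within a year, and the mixed models could absorb repeat seasons. The plan commits to neither for the main comparison.

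**Conclusion.** The point holds as an omission with two modest consequences, and no assumption is needed to establish that omission.

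For subjects randomised within the prior-vaccination stratum, ignoring it does not bias the comparison. It makes the unadjusted test conservative (about 3%-4%) and costs about 2-8 points of power relative to a stratified analysis, if the stratum effect is 0.5-1.0 SD. First-year subjects were not stratified this way, so adjustment helps there for balance too.

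If returners are mixed in, the arms most affected are HD in its first season (about 1%-16% in fold-rise ratio against SD or Flublok) and Flucelvax after closure. Egg versus recombinant shifts by about 1%-5%. Fluzone SD against Flublok is not affected by arms opening or closing, only by differential return. Every driver of these figures is assumed.

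Two stronger inferences are not supported. Season confounding and an error rate of up to about 11% need both pooling of seasons and treatment of person-seasons as independent. The plan states neither: naming years 1-5 in Section 4.2.1 does not require pooling. Nor can the wording of Section 8.2, which speaks of randomising only those not vaccinated with the prior year's vaccine, be taken to mean that all new subjects were unvaccinated, since Section 5 randomises both strata. That is a contradiction to reconcile. In a study that Section 12.2 itself calls explorative, this is a change that should be made, not a defect that invalidates the design.

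**What to change.** In Section 12.4:

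- Base the primary comparison on each participant's first, randomised season, between arms open to randomisation at the same time, with the prior-vaccination stratum as a factor. Add season as a factor if seasons are pooled.
- Analyse returning seasons under the repeat-vaccination objective with a participant random effect, and state whether antibody outcomes are included there.
- Give an all-seasons model with stratum, season and a participant random effect as a sensitivity analysis.
- State where Fluzone HD and Flucelvax fall in the group definitions.

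Separately, reconcile Section 8.2 with Section 5 on which subjects are randomised.

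The cost is SAP wording and one reconciled sentence. Vaccination history is already collected at screening, so no new data are needed. The downside is fewer records in the primary comparison, because returning and non-concurrent seasons move to the other analyses.

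### Vaccine comparisons in section 12.4 do not use the Day 0 value as a continuous covariate or name the randomisation stratum; adjusting would cost no data and usually gain precision

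*Combined protocol and SAP*

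**What the plan says.** Section 4.2.1 defines both primary outcomes as changes from Day 0. The first is "Mean change in the specificity, quantity and quality of serum antibody titers to the vaccine viruses", taken to Day 28. The second is CD4 T cell reactivity, which "will be quantified using cytokine Elispot From Day 0 to Day 14".

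Section 12.4 works on the log scale. For the outcomes it lists, "we will use maximum responses or maximum boost responses" (maximum after Day 0 minus Day 0) or maximum fold increase, and "do group comparison by ANOVA for among-group comparison and two-sample t-test for between-group comparison", with rank tests as alternatives. The comparisons are made overall and within pH1N1 seronegative and seropositive subjects. They are also said to be "based on both standard statistical analysis approaches using summary statistics and the complicated random variance model approach"; the covariates of that second approach are not given.

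The mixed-model paragraph of 12.4 enters group as a predictor and uses a "difference from difference approach to control the effect of baseline values". On covariates it says "Demographic information may be controlled by entering the model as predictors". Baseline values also appear in correlation tests, which are not vaccine comparisons.

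Sections 3.2 (second part) and 5 make prior-vaccination history the stratifier for randomisation. Section 3.1 says that antibody responses are weaker in people who start with higher titres, and that prior vaccinees tend to respond less vigorously.

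**The concern.** None of the planned vaccine comparisons has a continuous Day 0 covariate. The boost and the fold increase subtract the whole baseline, which is optimal only if the post-vaccination value rises one for one with it. The maximum response ignores baseline, which is optimal only if the two are unrelated. The pH1N1 split is coarse and does not address H3, influenza B or CD4. Section 3.2 also reports that few low-titre subjects could be found, so one side of the split may be sparse. The difference-from-difference step in the mixed model is again a change score unless baseline means are constrained to be equal across arms, and the plan does not say that they are.

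The protocol itself names baseline titre and prior vaccination as influences on the antibody response. What is at stake is precision at 45 per group. In addition, three endpoints are left open, and without adjustment they need not give the same answer.

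**Working it through.** **Inputs from the plan.** Section 12.2: 45 per group, two-sample t-test, two-sided 0.05, 80% power, CV of 0.25 to 0.4, stated detectable difference 10% to 20%.

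**The plan's own figure.** With 45 per group and 80% power, the t-test detects 0.597 SD. On the raw scale that is 0.597 × 0.25 = 14.9% to 0.597 × 0.4 = 23.9%, so the stated 10% to 20% is not reproduced. That is a separate matter and does not enter the comparison below. The plan gives no figure for the effect of baseline adjustment.

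**Assumed inputs.** The documents give neither the baseline-to-post correlation ρ nor the SD ratio k (post over baseline). I use ρ = 0.3, 0.5, 0.7 and k = 0.8, 1, 1.25, with one post-vaccination value per subject on the log scale.

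**Formulas** (baseline SD = 1):
- Change score: 1 + k² − 2ρk
- Post value only: k²
- ANCOVA on baseline: k²(1 − ρ²), ignoring the small loss of degrees of freedom
- n per group to match ANCOVA at 45: 45 × variance ÷ ANCOVA variance

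**Equal SDs (k = 1):**

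| ρ | Change | Post only | ANCOVA | ANCOVA ÷ change | ANCOVA ÷ post | n, change | n, post |
|---|---|---|---|---|---|---|---|
| 0.3 | 1.40 | 1.00 | 0.91 | 65% | 91% | 69.2 | 49.5 |
| 0.5 | 1.00 | 1.00 | 0.75 | 75% | 75% | 60.0 | 60.0 |
| 0.7 | 0.60 | 1.00 | 0.51 | 85% | 51% | 52.9 | 88.2 |

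**Other SD ratios, change score:**
- k = 0.8: 89.6, 78.8 and 71.7 for ρ = 0.3, 0.5, 0.7. For example, at ρ = 0.3, 1.16 ÷ 0.5824 × 45 = 89.6.
- k = 1.25: 57.4, 50.4 and 45.9.

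The post-only figures do not depend on k.

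**Does taking a maximum over visits remove the gain?** I simulated 400,000 subjects per cell with equal means and SDs. The assumed correlation between post-vaccination visits was 0.7 for two visits and 0.6 for four (0.7 when ρ = 0.7). For two titre visits (Days 28 and 180), the n to match is 72, 62, 55 for boost and 50, 62, 98 for maximum response. For four CD4 visits (Days 3, 7, 14, 180) it is 76, 66, 56 and 51, 66, 107. The gain remains.

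**What the stratum adds.** I simulated 45 per arm with balanced strata, a stratum shift of 0.7 SD in baseline and a direct effect on the outcome of 0 or 0.3 SD (all assumed). Once Day 0 was in the model, adding the stratum changed the variance of the vaccine estimate by less than 1%.

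**Effect on the choice of endpoint.** Log fold increase equals log maximum minus log Day 0. With log Day 0 as a covariate, the subtraction alters only the Day 0 coefficient, so the arm estimate and its p-value are identical for the two endpoints. The same identity means that ANCOVA on log Day 28 titre gives the same arm effect as ANCOVA on log change, and the mean-change comparison of section 4.2.1 is kept. A boost computed on the raw scale is a different endpoint and is not brought into line.

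**The case against.** The strongest reply is that nothing here is an error. Randomisation makes the unadjusted tests valid, section 4.2.1 itself specifies mean change, section 12.2 calls the study explorative, and the mixed models address baseline. All of that stands, except that the mixed-model step addresses baseline by subtraction and so does not deliver the gain as written.

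The second reply is that the size is not known. This also stands: ρ and k are assumptions, and at ρ = 0.7 and k = 1.25 a change score loses almost nothing. Section 3.1 supports dependence on baseline for serum antibody. For CD4 counts, on which the power statement rests, it is an assumption.

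A reader might infer more than the documents support:
- **That the planned tests are biased or inflate type I error.** Averaged over randomisations, each single test is not inflated. A test that ignores a prognostic stratum used in balanced blocks is, if anything, conservative.
- **That baseline imbalance explains the first-year result.** Section 3.2 reports higher pre-vaccination titres and more prior vaccination in the Fluzone group, but it also points to the dose difference. The documents do not separate these.
- **That the stratum brings precision.** It adds almost nothing beyond Day 0.
- **That covariates settle the endpoint choice.** They do so only between log maximum and log fold increase.

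**Conclusion.** The point holds as an improvement at no data cost, not as a flaw in validity. With equal SDs and ρ from 0.3 to 0.7, a change score needs about 69 to 53 per group to match ANCOVA at 45, and a post-only endpoint about 49 to 88. Over SD ratios of 0.8 to 1.25 the change-score figure runs from about 90 down to 46, so the gain ranges from a doubling of n to almost nothing.

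These figures rest on assumed correlations and SD ratios, a linear relation on the log scale, and newly randomised subjects. The reason to include the stratum is agreement between analysis and randomisation.

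**What to change.** 1. For newly randomised subjects, name one endpoint and one scale per outcome. Log Day 28 titre and log Day 14 ELISPOT match section 4.2.1. Compare arms by ANCOVA with the log Day 0 value of the same assay as a continuous covariate.
2. Include the prior-vaccination stratum, and state that it is there to match the randomisation.
3. In the mixed model, add the stratum and constrain baseline means to be equal across randomised arms.
4. Analyse re-enrolled subjects separately. They keep their earlier vaccine, so their later Day 0 value may already reflect it, and the equal-baseline constraint is not justified for them.
5. Before defining the stratum term, reconcile section 5, which randomises both history groups, with section 8.2, which states randomisation only for subjects who did not have the prior year's vaccine. Read literally, section 8.2 would make the term constant among those randomised.

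The cost is SAP wording, a rule separating first-enrolment from re-enrolled records, and the reconciliation in item 5. Day 0 samples and vaccination history are already collected, so no visits, samples or subjects are added.
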